7.1.3. Population of Interest

PK population.

7.1.4. Strategy for Intercurrent Events

Participants who experienced the following intercurrent events will have data from the relevant treatment period excluded from analysis:

- Received incorrect formulation or meal
- Did not consume at least 90% of the meal (in fed participants)
- Did not provide an adequate PK concentration profile to allow reliable estimation of PK parameters

Inclusion of the participant's remaining data in the analysis effectively uses a missing at random assumption to account for the excluded data.

If a participant is included in the PK population but withdrew from the study prior to a treatment period, data for that and subsequent periods will not be imputed. Inclusion of the participant's data prior to withdrawal in the analysis effectively uses a missing at random assumption to account for the missing data.

7.1.5. Statistical Analyses / Methods

Details of the planned displays are provided in [Appendix 10](#): List of Data Displays and will be based on GSK Data Standards and statistical principles.

7.1.5.1. Statistical Methodology Specification

Endpoint / Variables

 Log-transformed AUC(0-inf) and Cmax in fed and fasted states. Log-transformed AUC(0-t), AUC(0-24) and t1/2 in fed and fasted states.
Model Specification

 Include all Part A data in the model. Mixed effects model with fixed effect terms for period and treatment (formulation and fed/fasted state). Participant will be treated as a random effect in the model. Point estimates on the \log_e scale for the least squares (LS) mean for each treatment and the LS mean difference between treatments (for comparisons specified in Section 7.1.2: Summary Measure), and associated 90% CI for the difference will be constructed using the residual variance. The LS means, LS mean differences and associated 90% CIs will then be back-transformed to obtain geometric LS mean for each treatment, and LS treatment ratios and associated 90% CIs. The Kenward and Roger method for approximating the denominator degrees of freedom and correcting for bias in the estimated variance-covariance of the fixed effects will be used.
Model Checking & Diagnostics

 Model assumptions will be applied, but appropriate adjustments maybe made based on the data. Distributional assumptions underlying the model used for analysis will be examined by obtaining a normal probability plot of the residuals and a plot of the residuals versus the fitted values (i.e. checking the normality assumption and constant variance assumption of the model respectively) to gain confidence that the model assumptions are reasonable. If there are any departures from the distributional assumptions, alternative models will be explored using appropriate transformed data.
Model Results Presentation

 Separate outputs will be produced for fed and fasted states (although both will be analyzed using the same model) Geometric LS means for each treatment, treatment ratios and associated 90% CIs for each parameter. Estimates of within-participant variability (%CVw) for AUC and Cmax (%CVw represents a pooled measure of within-participant variability across treatments). Comparative plots of individual blood PK parameters by treatment on linear and semi-logarithmic scales. Forest plots of geometric mean treatment ratios for AUC and Cmax together with 90% CIs. Listing of individual blood PK parameter ratios. Supportive SAS output from statistical analysis.

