7.1.2. Summary Measure

Relative bioavailability of danirixin after single dose of three formulations of HBr tablet (DC) versus HBr tablet (RC) in fed and fasted states.

- Fed (treatment comparisons B vs A, C vs A, D vs A)
- Fasted (treatment comparisons BO vs AO, CO vs AO, DO vs AO)

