7.2.2. Summary Measure

Relative bioavailability of danirixin after single dose.

- Food effect in test formulation (treatment comparisons A vs AO, B vs BO, C vs CO, D vs DO)
- Food effect in selected formulation without PPI (treatment comparisons G vs E, F vs E, G vs F)
- Food effect in selected formulation with PPI (treatment comparisons K vs I, J vs I, K vs J)
- PPI effect in selected formulation (treatment comparisons I vs E, J vs F, K vs G)
- Pharmaceutical development (treatment comparison H vs G)

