7.2.5.1. Statistical Methodology Specification

Secondary PK analyses will use the same methods as described in Section [7.1: Primary Pharmacokinetic Analysis](#). The data to be included in each model are described below.

Food Effect in Test Formulations
Treatment Comparisons

• A vs AO, B vs BO, C vs CO, D vs DO
Model Specification

• From model used for primary PK analysis including all Part A data.

Food Effect in Selected Formulation without PPI
Treatment Comparisons

• G vs E, F vs E, G vs F
Food Effect in Selected Formulation with PPI
Treatment Comparisons

• K vs I, J vs I, K vs J
PPI Effect in Selected Formulation
Treatment Comparisons

• I vs E, J vs F, K vs G
Model Specification

• Include all Part B data from periods 1-3.

Pharmaceutical Development
Treatment Comparisons

• H vs G
Model Specification

• Part B non-OMP treatment arms (E-H) only.• Estimates presented for treatments G and H and difference H vs G.

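### The SAP carries a residual-variance rule for confidence intervals over to seven contrasts between different participants, where that rule is wrong and conflicts with the specified Kenward-Roger covariance

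*SAP*

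**What the plan says.** SAP 7.1.5.1 fits a mixed model to the log-transformed parameters, with period and treatment as fixed effects: "Participant will be treated as a random effect in the model". It states that the "associated 90% CI for the difference will be constructed using the residual variance", and ties the differences in question to a list: "for comparisons specified in Section 7.1.2: Summary Measure". The same section specifies Kenward-Roger for the denominator degrees of freedom and for "correcting for bias in the estimated variance-covariance of the fixed effects will be used".

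SAP 7.1.2 lists six comparisons: "Fed (treatment comparisons B vs A, C vs A, D vs A", and the fasted counterparts BO, CO and DO vs AO.

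SAP 7.2.5.1 opens with "Secondary PK analyses will use the same methods as described in Section" 7.1, and then restates only which data enter each model. For the Part A food effect that is "From model used for primary PK analysis including all Part A data". For the Part B food and omeprazole (OMP) contrasts it is all Part B data from periods 1 to 3. No separate variance rule is given. SAP 7.2.2 lists the contrasts, including "PPI effect in selected formulation (treatment comparisons I vs E, J vs F, K vs G".

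On the design, Protocol 5.1 and 7.3 and SAP 2.3 put different people in the two groups of each part. In Part A, Group 1 is fed in every period and Group 2 is fasted in every period. In Part B, Group 1 receives E to H without OMP, and Group 2 receives I to K while taking OMP throughout.

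**The concern.** In a within-participant contrast each person's own level cancels, and only residual variance remains. In a contrast between two groups of different people it does not cancel, and the variance of the difference contains the between-participant component as well.

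SAP 7.2.5.1 covers 14 contrasts. Seven are within participant (G vs E, F vs E, G vs F, K vs I, J vs I, K vs J, H vs G). The other seven have no participant in common: A vs AO, B vs BO, C vs CO, D vs DO, I vs E, J vs F and K vs G. For these, the carried-over rule and the model covariance in 7.1.5.1 give different standard errors, and the SAP does not say which governs.

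The 90% interval is the stated inferential output, since SAP 2.4 plans no hypothesis test. The seven contrasts supply every OMP-effect comparison, a stated Part B objective, and the Part A food effect by formulation. Each set has its own table and forest plot in SAP Appendix 10.

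**Working it through.** **Inputs**

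- Within-participant CV (Protocol 10.1): 37.3% for AUC(0-inf), 44.7% for Cmax. On the log scale σw² = ln(1 + CV²), which is 0.130 and 0.182.
- Completers per group (Protocol 10.1): 6 in Part A, 10 in Part B.
- Between-participant CV (CVb): not in the documents. **Assumed** at 20% to 60%, with σb² = ln(1 + CVb²), e.g. 0.039 at 20%, 0.148 at 40% and 0.307 at 60%.
- Error degrees of freedom with complete data: 6n − 9 = 27 in Part A (n = 6, four periods, both groups); 4n − 6 = 34 in Part B (n = 10, periods 1 to 3).

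**The protocol's own figure.** Protocol 10.1 gives 0.70 to 1.42 for an observed ratio of 1 with 6 completers. This reproduces as exp(± t(0.95, 5) × 0.4268/√6) = 0.704 to 1.421. That form uses within-participant variance only. It also leaves out the factor √2 for a difference of two means, which is a separate matter. It says nothing about the precision of contrasts between groups.

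**Variance of the two kinds of contrast.** With complete data:

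- within participant (e.g. B vs A): 2σw²/n
- between participants (e.g. A vs AO): 2(σw² + σb²)/n

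Generalised least squares on the SAP sequences, with period and treatment fixed and participant random, confirms both forms. For Cmax at CVb 50%:

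| Setting | Within-participant contrast | Between-participant contrast |
|---|---|---|
| Part A, 8 per group | B vs A: 0.0455 | A vs AO: 0.1013 |
| Part B, 12 per group | G vs E: 0.0304 | I vs E: 0.0676 |

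**Understatement and coverage if only residual variance is used.** The standard error is too small by the factor √((σw² + σb²)/σw²). True coverage is P(|T| < t(0.95, df) × √(σw²/(σw² + σb²))), with T on df degrees of freedom. Part A and Part B agree to within one percentage point.

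| Assumed CVb | Cmax: factor | Cmax: coverage | AUC(0-inf): factor | AUC(0-inf): coverage |
|---|---|---|---|---|
| 20% | 1.10 | 87% | 1.14 | 85% |
| 30% | 1.21 | 83% | 1.29 | 80% |
| 40% | 1.35 | 78% | 1.46 | 75% |
| 50% | 1.49 | 74% | 1.65 | 69% |
| 60% | 1.64 | 69% | 1.83 | 64% |

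**Interval widths, Cmax at ratio 1.** The residual-only half-width is t(0.95, df) × √(2σw²/n). In Part A this is 1.703 × √(2 × 0.182/6) = 0.42, giving 0.66 to 1.52. The full-variance half-width is t × √(2(σw² + σb²)/n) with Satterthwaite degrees of freedom. In Part A at CVb 40% these are 24.5, and the half-width is 1.71 × √(2 × 0.331/6) = 0.57, giving 0.57 to 1.76.

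| Part, completers per group | Assumed CVb | Residual only | Full variance |
|---|---|---|---|
| A, 6 | 20% | 0.66–1.52 | 0.63–1.58 |
| A, 6 | 40% | 0.66–1.52 | 0.57–1.76 (df 24.5) |
| B, 10 | 20% | 0.72–1.38 | 0.70–1.42 |
| B, 10 | 40% | 0.72–1.38 | 0.65–1.54 (df 38.2) |

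**Simulation check.** 3,000 trials per case on the SAP sequences, fitted by REML with the SAP's fixed and random effects, Cmax CV 44.7%:

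| Contrast | CVb | SE: mixed model / residual only | Coverage: mixed model / residual only |
|---|---|---|---|
| A vs AO | 20% | 0.270 / 0.243 | 90% / 86% |
| A vs AO | 40% | 0.328 / 0.244 | 91% / 79% |
| A vs AO | 60% | 0.398 / 0.245 | 89% / 69% |
| I vs E | 20% | 0.209 / 0.188 | 91% / 87% |
| I vs E | 40% | 0.255 / 0.189 | 90% / 78% |
| I vs E | 60% | 0.310 / 0.189 | 90% / 69% |

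A separate run of 20,000 simulated Part A trials at CVb 50% gave 73.8% coverage for residual-only and 90.1% for full variance.

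**The case against.** The strongest reply is that the SAP does not really prescribe the wrong interval. The residual-variance sentence is already confined to the 7.1.2 comparisons. The natural meaning of the carry-over is the model, since 7.2.5.1 goes on to speak of the data for each model and takes the Part A food contrasts from the primary one. That model has a random participant effect and a Kenward-Roger covariance, so a contrast estimated from it has the right standard error by default. The SAP plans supportive SAS output for these analyses (Listings 35 and 36) and nowhere describes a hand-built interval. Because excluded periods are foreseen in 7.1.4, even the primary contrasts need not equal a residual-only formula, which points to loose wording rather than a second rule. The size of the error rests on an assumed CVb and is small at 20%. The contrasts are secondary and untested, and none is named among the criteria for selecting the formulation.

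Much of this stands. The reported intervals may well be right, the primary contrasts are not affected, and the magnitude is conditional. It does not remove the defect. Section 7.2.5.1 imports the methods without qualification and offers no other variance rule, and 7.1.5.1 contains an explicit statement of how the interval is built. A programmer who follows that statement and one who takes the model covariance will get different intervals for the seven contrasts, and a quality check against the SAP could support either. The direction of the error does not depend on CVb: any between-participant variance above zero makes the residual-only interval too narrow.

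**Conclusion.** The concern holds. As written, the SAP extends a rule that is right for the six primary contrasts to seven between-participant contrasts where it is wrong, and where it contradicts the Kenward-Roger covariance it also specifies. It does not follow that the published intervals will be too narrow; that depends on which rule is programmed. If it is the residual-variance rule, nominal 90% intervals cover about 87% to 69% for Cmax and 85% to 64% for AUC(0-inf) as the assumed CVb rises from 20% to 60%. If the mixed-model standard error is used, coverage is about 90%. These figures assume complete data at the planned completer numbers, the protocol's within-participant CVs, and a CVb range that the documents do not supply. The point should be fixed, but it does not touch the primary relative-bioavailability results.

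**What to change.** In SAP 7.1.5.1, limit the residual-variance construction to within-participant (within-group) contrasts. In SAP 7.2.5.1, state that A vs AO, B vs BO, C vs CO, D vs DO, I vs E, J vs F and K vs G are comparisons between different participants, and that their 90% intervals use the mixed-model standard error of the contrast (participant plus residual variance) with Kenward-Roger degrees of freedom.

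The cost is one or two sentences. No new model, data or participants are needed, because the specified model already yields this standard error. The only downside is that these secondary intervals are wider than under the residual-only rule.

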7.2. Secondary Pharmacokinetic Parameter Analyses

The following analyses will be conducted to assess food effect, PPI effect and pharmaceutical development. The primary treatment effect to be estimated is the 'as-treated effect of the treatment (formulation and meal) in participants who consume at least 90% of the meal (in fed participants), are OMP compliant (in OMP participants) and provided an adequate PK concentration profile to allow reliable estimation of PK parameters.

7.2.1. Endpoint / Variables

- Log-transformed AUC(0-inf) and Cmax.
- Log-transformed AUC(0-t), AUC(0-24) and t1/2.

7.2.2. Summary Measure

Relative bioavailability of danirixin after single dose.

- Food effect in test formulation (treatment comparisons A vs AO, B vs BO, C vs CO, D vs DO)
- Food effect in selected formulation without PPI (treatment comparisons G vs E, F vs E, G vs F)
- Food effect in selected formulation with PPI (treatment comparisons K vs I, J vs I, K vs J)
- PPI effect in selected formulation (treatment comparisons I vs E, J vs F, K vs G)
- Pharmaceutical development (treatment comparison H vs G)

7.2.3. Population of Interest

PK population.

7.2.4. Strategy for Intercurrent Events

Participants who experienced the following intercurrent events will have data from the relevant treatment period excluded from analysis:

- Received incorrect formulation or meal
- Did not consume at least 90% of the meal (in fed participants)
- Missed more than one OMP dose between Days -4 and -2 or missed any other OMP dose (participants on treatments I, J, K – Section 5.1 Study Treatment Display Descriptors))
- Did not provide an adequate PK concentration profile to allow reliable estimation of PK parameters

Inclusion of the participant's remaining data in the analysis effectively uses a missing at random assumption to account for the excluded data.

If a participant is included in the PK population but withdrew from the study prior to a treatment period, data for that and subsequent periods will not be imputed. Inclusion of

the participant's data prior to withdrawal in the analysis effectively uses a missing at random assumption to account for the missing data.

7.2.5. Statistical Analyses / Methods

Details of the planned displays are provided in [Appendix 10: List of Data Displays](#) and will be based on GSK Data Standards and statistical principles.

7.2.5.1. Statistical Methodology Specification

Secondary PK analyses will use the same methods as described in Section [7.1: Primary Pharmacokinetic Analysis](#). The data to be included in each model are described below.

Food Effect in Test Formulations
Treatment Comparisons

• A vs AO, B vs BO, C vs CO, D vs DO
Model Specification

• From model used for primary PK analysis including all Part A data.

Food Effect in Selected Formulation without PPI
Treatment Comparisons

• G vs E, F vs E, G vs F
Food Effect in Selected Formulation with PPI
Treatment Comparisons

• K vs I, J vs I, K vs J
PPI Effect in Selected Formulation
Treatment Comparisons

• I vs E, J vs F, K vs G
Model Specification

• Include all Part B data from periods 1-3.

Pharmaceutical Development
Treatment Comparisons

• H vs G
Model Specification

• Part B non-OMP treatment arms (E-H) only.• Estimates presented for treatments G and H and difference H vs G.

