
 To estimate the effect of OMP on the single dose pharmacokinetics of the danirixin HBr tablet formulation selected from Part A in healthy elderly participants in various fed and fasted states. 	
 Danirixin PK parameters: AUC(0-inf), AUC(0-t), AUC(0-24), Cmax, tmax, t1/2, tlast and tlag. 	Part B

Objectives	Endpoints	Part

 To estimate the relative bioavailability of danirixin after single dose administration of HBr tablet (RC), the reference treatment, relative to the test formulation of the HBr tablet (MONO), in healthy elderly participants in the fed state. 	
 Danirixin PK parameters: AUC(0-inf), AUC(0-t), AUC(0-24), Cmax, tmax, t1/2, tlast and tlag. 	Part B

 To provide safety and tolerability information for oral administration of danirixin HBr tablets in elderly participants. 	
 AEs/SAEs, vital signs, ECGs, and clinical laboratory parameters 	Part B

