Treatment Assignment	
 In Part A, 16 participants were randomised to a treatment sequence including treatments A-D or AO-DO (Section 5.1: Study Treatment Display Descriptors). Participants randomised to a treatment sequence including treatments A-D comprised Group 1 and participants randomised to a treatment sequence including treatments AO-DO comprised Group 2. Equal numbers of participants were randomized to each of the following sequences: 
 
ABCD	
 
BDAC	
 
CADB	
 
DCBA	
 
AOBOCODO	
 
BODOAOCO	
 
COAODOBO	
 
DOCBOAO	
 
 In Part B, Group 1, 12 participants were randomised to a treatment sequence including treatments E-H (Section 5.1: Study Treatment Display Descriptors). Equal numbers of participants were randomized to each of the following sequences: 
 
EFGH	
 
EGFH	
 
FGEH	
 
FEGH	
 
GEFH	
 
GFEH	
 
 In Part B, Group 2, 12 participants were randomised to a treatment sequence including treatments I-K (Section 5.1: Study Treatment Display Descriptors). Equal numbers of participants were randomized to each of the following sequences: 
 
IJK	
 
IKJ	
 
JKI	
 
JIK	
 
KIJ	
 
KJI	
 
 
 • GSK RandAll NG was used to generate the randomisation schedules. • Study treatment was dispensed to participants at the study visits according to the randomisation schedule. 
	ABCD	BDAC	CADB	DCBA	AOBOCODO	BODOAOCO	COAODOBO	DOCBOAO	EFGH	EGFH	FGEH	FEGH	GEFH	GFEH	IJK	IKJ	JKI	JIK	KIJ	KJI
ABCD																					
BDAC																					
CADB																					
DCBA																					
AOBOCODO																					
BODOAOCO																					
COAODOBO																					
DOCBOAO																					
EFGH																					
EGFH																					
FGEH																					
FEGH																					
GEFH																					
GFEH																					
IJK																					
IKJ																					
JKI																					
JIK																					
KIJ																					
KJI																					

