10.10.5. Pharmacokinetic Tables

Pharmacokinetic: Tables					
No.	Population	IDSL / Example Shell	Title	Programming Notes	Deliverable [Priority]
2.1.	PK	PK01	Summary of Danirixin Blood Pharmacokinetic Concentration-Time Data	Split by Part, Group and by treatment	SAC
2.2.	PK	PK03	Summary Statistics of Untransformed Derived Danirixin Blood Pharmacokinetic Parameters	Split by Part, Group and by treatment	SAC
2.3.	PK	PK05	Summary Statistics of Log-transformed Derived Danirixin Blood Pharmacokinetic Parameters	Split by Part, Group and by treatment	SAC
2.4.	PK	201037 Table 3.6	Summary of Statistical Analysis of Log-transformed Danirixin Blood Pharmacokinetic Parameters: Fed State	Part A	SAC
2.5.	PK	201037 Table 3.6	Summary of Statistical Analysis of Log-transformed Danirixin Blood Pharmacokinetic Parameters: Fasted State	Part A	SAC
2.6.	PK	201037 Table 3.6	Summary of Statistical Analysis of Log-transformed Danirixin Blood Pharmacokinetic Parameters: Food Effect in Test Formulations	Part A	SAC
2.7.	PK	201037 Table 3.6	Summary of Statistical Analysis of Log-transformed Danirixin Blood Pharmacokinetic Parameters: Food Effect in Selected Formulation without Proton Pump Inhibitor	Part B	SAC
2.8.	PK	201037 Table 3.6	Summary of Statistical Analysis of Log-transformed Danirixin Blood Pharmacokinetic Parameters: Food Effect in Selected Formulation with Proton Pump Inhibitor	Part B	SAC
2.9.	PK	201037 Table 3.6	Summary of Statistical Analysis of Log-transformed Danirixin Blood Pharmacokinetic Parameters: Proton Pump Inhibitor Effect in Selected Formulation	Part B	SAC

Pharmacokinetic: Tables					
No.	Population	IDSL / Example Shell	Title	Programming Notes	Deliverable [Priority]
2.10.	PK	201037 Table 3.6	Summary of Statistical Analysis of Log-transformed Danirixin Blood Pharmacokinetic Parameters: Pharmaceutical Development	Part B	SAC

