2.14.	PK	201037 Figure 3.7	Geometric Mean (90% CI) Treatment Ratios of Danirixin Blood Pharmacokinetic Parameters Food Effect in Test Formulations	Treatment comparisons A vs AO, B vs BO, C vs CO, D vs DO	SAC
2.15.	PK	201037 Figure 3.7	Geometric Mean (90% CI) Treatment Ratios of Danirixin Blood Pharmacokinetic Parameters Food Effect in Selected Formulation without Proton Pump Inhibitor	Treatment comparisons G vs E, F vs E, G vs F	SAC
2.16.	PK	201037 Figure 3.7	Geometric Mean (90% CI) Treatment Ratios of Danirixin Blood Pharmacokinetic Parameters: Food Effect in Selected Formulation with Proton Pump Inhibitor	treatment comparisons K vs I, J vs I, K vs J	SAC

Pharmacokinetic: Figures					
No.	Population	IDSL / Example Shell	Title	Programming Notes	Deliverable [Priority]
2.17.	PK	201037 Figure 3.7	Geometric Mean (90% CI) Treatment Ratios of Danirixin Blood Pharmacokinetic Parameters: Proton Pump Inhibitor Effect in Selected Formulation	Treatment comparisons I vs E, J vs F, K vs G	SAC
2.18.	PK	201037 Figure 3.7	Geometric Mean (90% CI) Treatment Ratios of Danirixin Blood Pharmacokinetic Parameters: Pharmaceutical Development	Treatment comparison H vs G	SAC

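### The monohydrate comparison (H vs G) cannot be estimated by the model the SAP specifies, because H is given only in period 4 and period 4 contains only H

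*SAP*

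**What the plan says.** SAP Section 2.3 (Treatment Assignment) states: "In Part B, Group 1, 12 participants were randomised to a treatment sequence including treatments E-H". The sequences it then lists are EFGH, EGFH, FGEH, FEGH, GEFH and GFEH, with equal numbers on each, so two participants per sequence. E, F and G are permuted over periods 1 to 3, and H is always fourth.

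SAP Section 7.2.5.1 sets the method for all secondary comparisons by reference: "Secondary PK analyses will use the same methods as described in Section" 7.1. Section 7.1.5.1 gives that method as a "Mixed effects model with fixed effect terms for period and treatment (formulation and fed/fasted state"), with participant random. The LS means, their differences and the 90% CIs come from this model.

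The food-effect and PPI comparisons use Part B data from periods 1 to 3. The monohydrate comparison has its own model, with data from "Part B non-OMP treatment arms (E-H) only" and the stated output "Estimates presented for treatments G and H and difference H vs G". The results go to Table 2.10 ("Summary of Statistical Analysis of Log-transformed Danirixin Blood Pharmacokinetic Parameters: Pharmaceutical Development") and Figure 2.18 ("Geometric Mean (90% CI) Treatment Ratios of Danirixin Blood Pharmacokinetic Parameters: Pharmaceutical Development"). Neither document removes period from this model or mentions that H occurs in one period only.

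On a separate point of wording, the Part B objective in SAP Section 2.2 names its reference as "HBr tablet (RC), the reference treatment, relative to the test formulation of the HBr tablet (MONO"), whereas the planned contrast takes G as its reference. Protocol Table 5 defines G as the formulation selected from Part A, given with the high-fat meal.

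**The concern.** A period effect can be separated from a treatment effect only if the treatment appears in more than one period, or the period contains more than one treatment. In Group 1 neither is true of H and period 4. A model that fits both terms has two names for one quantity, and nothing in the data can divide it between them.

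H vs G is the only planned comparison for the Part B monohydrate objective, and Table 2.10 and Figure 2.18 are its only model-based displays (Listing 37 is SAS output from the same model). Run as written, the program would either flag the estimates as non-estimable or return a value fixed by an arbitrary constraint. If an analyst removed period without saying so, the report would show an H/G ratio with a 90% CI and no indication that any period-4 effect is inside it.

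**Working it through.** The documents give no figure for H vs G, so the check is one of estimability.

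**Inputs.** Sequences and group size: SAP 2.3. Model terms: SAP 7.1.5.1, carried over by 7.2.5.1. Data included: arms E to H, which is 12 participants × 4 periods = 48 rows. Within-subject CV of 44.7% for Cmax: protocol Section 10.1.

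**1. Algebra.** On the log scale the model is E[y] = μ + π(period) + τ(treatment). Every H observation has expectation μ + π4 + τH, and no other observation contains π4 or τH. Add any constant c to π4 and subtract it from τH, and every expected value is unchanged. However:

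- H − G = τH − τG changes by −c.
- LS mean of G = μ + (π1+π2+π3+π4)/4 + τG changes by +c/4, as do those of E and F.
- LS mean of H changes by c/4 − c = −3c/4.

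None of these is determined by the data. G − E, F − E and G − F do not change, so they remain estimable.

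**2. Rank check.** Each fixed-effects matrix was built from the listed sequences. The rank needed is 1 + (periods − 1) + (treatments − 1).

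| Model | Rank needed | Rank found |
|---|---|---|
| Part B Group 1, E–H, with period | 1+3+3 = 7 | 6 |
| Part B periods 1–3, both groups | 1+2+5 = 8 | 8 |
| Part A, all data | 1+3+7 = 11 | 11 |
| All Part B data, four periods | 1+3+6 = 10 | 9 |
| E–H, treatment only | 4 | 4 |

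The shortfall is the same with participant fixed instead of random. Pooling in Group 2 does not help, because that group has only three periods.

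**3. Could conduct of the trial break the aliasing?** No. Periods with the wrong formulation are excluded (SAP 7.2.4), and replacements take the same sequence (SAP 10.7.1). With 15% of periods removed at random, H − G was estimable in 0 of 2000 draws.

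**4. Illustration.** In one simulated dataset, fixing the period-4 effect at a ratio of 0.8, 1.0 or 1.25 gave H/G of 1.70, 1.36 or 1.09. The residual sum of squares was 16.907679 each time, so the fit cannot choose between them.

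**5. Without the period term.** With complete data, the H − G estimate is the mean within-participant difference. G falls in each of periods 1, 2 and 3 four times, so its expectation is

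(τH − τG) + [π4 − (π1+π2+π3)/3].

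Any period-4 effect passes one-for-one into the ratio.

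**6. Precision of that model at an observed ratio of 1.** σ² = ln(1 + 0.447²) = 0.182; SE = √(2σ²/n); df = 3(n − 1).

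- n = 10: SE 0.191, t(27) = 1.703, log half-width 0.325, 90% CI 0.722 to 1.384.
- n = 12: SE 0.174, t(33) = 1.692, log half-width 0.295, 90% CI 0.745 to 1.343.

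**The case against.** The aliasing itself is hard to dispute. The reasonable objections concern latitude, extent, weight and remedy.

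- **Latitude.** SAP 7.1.5.1 allows adjustments to the model in the light of the data. That line sits under model checking, beside residual plots and transformations, and names no alternative. This problem comes from the planned sequences and is known before any data, so the line does not resolve it.
- **Extent for G.** G is observed in periods 1 to 3. Its mean over those periods is estimable, and the periods 1–3 model supplies a G mean for Table 2.7. That is right. What fails is the LS mean of G in the E–H model, averaged over all four periods, which is what Table 2.10 calls for.
- **Weight.** This is one secondary contrast, untested, and descriptive information on G and H survives in Tables 2.2 and 2.3, Figure 2.11 and Listing 14. Software would probably flag the failure. All true, and it limits the scope. It does not give the stated objective the estimate and 90% CI that SAP Section 2.4 promises for every comparison.
- **Remedy.** The bias expression in step 5 needs G spread equally over periods 1 to 3. Ten completers cannot be: two losses leave G split 4, 4, 2 or 4, 3, 3, so the weights become 0.4, 0.4, 0.2 or 0.4, 0.3, 0.3 instead of one third each. The change is small, but the no-period model then also assumes that periods 1 to 3 are alike, and the disclosure should say so. An alternative keeps the period 1–3 effects and sets period 4 equal to their mean. With complete data it gives the same H/G point estimate, and it copes better with imbalance. It rests on an equally untestable assumption about period 4.

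**Conclusion.** The concern holds. As specified, the E–H model cannot deliver the H/G ratio or the LS means for G and H. The rank deficit is exactly one, and it follows from the listed sequences and the two model terms alone; no assumption about variability or dropout enters.

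The scope is narrow: 1 of 20 planned contrasts. The 10 Part A contrasts and the 9 Part B food-effect and PPI contrasts come from full-rank models and are unaffected. Within that scope the defect must be corrected before analysis, because a specified output has no valid value and any workable substitute needs an assumption about period 4 that the SAP does not state.

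The 90% CIs of 0.72 to 1.38 (10 completers) and 0.74 to 1.34 (12) assume the protocol's Cmax CV, an observed ratio of 1 and no period-4 effect. The mismatch between the objective's RC reference and G is secondary. It arises only if RC is not the selected formulation, and the conclusion does not depend on it.

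**What to change.** In SAP Section 7.2.5.1, for the Pharmaceutical Development model only, specify treatment as fixed and participant as random, with no period term. Add a statement, repeated in the study report and as a footnote to Table 2.10 and Figure 2.18, along these lines:

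> H was given only in period 4, so the H/G ratio is confounded with any period-4 effect. The 90% CI assumes that there is none and, where data are incomplete, that periods 1 to 3 do not differ.

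Estimated period 1–3 effects may be shown as context, but they cannot test the period-4 effect. Leave the Part A and Part B periods 1–3 models unchanged. Unless RC is the selected formulation, reword the objective so that its reference is the selected formulation with the high-fat meal (G).

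Balancing H over the four periods would also restore estimability (rank 7 of 7), but the SAP describes randomisation as already done, so that route is not practical.

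The cost is two sentences, one term removed from one program and a footnote on two displays. The drawbacks are an explicit, untestable assumption for this contrast, and that any real differences among periods 1 to 3 move into this model's residual.
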